## List of abbreviations

AE	Adverse event
AESI	Adverse events of special interest
ALP	Alkaline phosphatase
ALT	Alanine aminotransferase
████████	████████
AST	Aspartate aminotransferase
ATC	Anatomical Therapeutic Classification
BMI	Body mass index
CDBL	Clinical database lock
CMD	Concomitant medication
CRF	Case Report Form
CSR	Clinical Study report
C-SSRS	Columbia-Suicide Severity Rating Scale
CTC	Common Toxicity Criteria
CTCAE	Common Terminology Criteria for Adverse Events
CTT	Clinical Trial Team
DMT	Disease Modifying Therapy
ECG	Electrocardiogram
eCRF	Electronic Case Report Form
eCRS	Electronic Case Retrieval Sheet
████████	████████
EOS	End of study
FACS	Fluorescence activated cell sorting
FAS	Full analysis set
FDA	Food and Drug Administration
FU	Follow-up
GdE	Gadolinium enhancing lesion
████████	████████
GPS	Global Programming and Statistical Environment
LLN	Lower limit of normal
LPLV	Last patient last visit
mAb	Monoclonal Antibody
MedDRA	Medical Dictionary for Drug Regulatory Affairs
MRI	Magnetic Resonance Imaging
MS	Multiple Sclerosis
NBS	Novartis Business Services
████████	████████
████	████
NRI	Non-responder imputation
PD	Protocol deviation
████████	████████
PK	Pharmacokinetics

PT	Preferred term
RAP	Report and Analysis Process
RMS	Relapsing Multiple Sclerosis
RRMS	Relapsing-remitting Multiple Sclerosis
SAE	Serious adverse event
SAF	Safety set
SAP	Statistical Analysis Plan
SOC	System Organ Class
SPMS	Secondary Progressive Multiple Sclerosis
TEAE	Treatment emergent adverse event
TSQM-9	Treatment Satisfaction Questionnaire for Medication
WHO	World Health Organization
WHODD	WHO Drug Dictionary

## 1 Introduction

The purpose of this Statistical Analysis Plan (SAP) is to describe the statistical methods planned in Section 12 of the clinical study protocol version 02 (release date 28 June 2022) for the clinical trial COMB157GUS07 and any additional analyses, specifications or deviations from this protocol planned before clinical database lock (CDBL).

The SAP will be used to draft the Clinical Study Report (CSR) Section 9.7: Statistical methods and IA plans.

### 1.1 Study design

This is a single-arm, multi-center, prospective study in patients with relapsing multiple sclerosis (RMS) who have been previously treated with anti-CD20 (aCD20) monoclonal antibody (mAb) therapy and have received at least 2 consecutive courses of intravenously administered ocrelizumab or rituximab every 6 months and the last dose is within 4 to 9 months before Baseline/Day 1.

In this study, participants may enroll only if discontinuing aCD20 therapy for reasons other than lack of efficacy or due to certain treatment-emergent adverse events. Reasons for switching may include but are not limited to physician/participant preference, access to commercial drug (e.g., insurance coverage issues) or for other logistical reasons (such as geographical relocation, travel, etc.).

A total of approximately 100 eligible participants will be enrolled as part of this study. Participants will receive open label ofatumumab 20 mg subcutaneous once monthly for 12 months following initial loading regimen of 20 mg subcutaneous doses on Days 1, 7 and 14.

For participants completing the trial, the total duration of the trial will be a minimum of 14 months. This accounts for the:

- 28 day screening period
- 12 month treatment period
- 30 day telephone safety follow-up

Participants are considered as having completed the study after completing the 12 month treatment period and attending the End of Study (EOS) visit. For participants who discontinue study treatment prematurely for any reason before the end of the 12 month treatment period, an EOS visit will be performed within 7 days of study discontinuation.

Additional post-treatment safety follow-up will be applicable for participants who:

[figure not shown]
- Complete the Treatment period and do not continue on any MS disease modifying therapy (DMT)
- Do not continue into the ofatumumab commercial patient services hub within one month of the End of Study (EOS) visit, where the EOS visit is defined as the last patient's last visit (LPLV), which is the last patient's Month 12 visit, or the visit scheduled at the time of study discontinuation.
- Prematurely discontinue study drug and do not continue on an MS DMT.

The post-treatment safety FU period will consist of visits every 3 months post EOS. Assessments will include B cell monitoring until participants are able to start on commercial ofatumumab or until they switch to another therapy or until their B cells are repleted, where B cell repletion is defined as a B cell concentration greater than the individual participant's baseline value prior to starting the IV anti-CD20 mAb or greater than the lower limit of normal.

All post-treatment safety FU visits will be scheduled relative to the EOS visit.

The following [Figure 1-1](#) describes the study design.

**Figure 1-1** Study design

## 1.2 Study objectives and endpoints

**Table 1-1** Study objectives and endpoints

Objectives(s)	Endpoint(s)
Primary objective(s) 

Explore maintenance of efficacy of ofatumumab in participants with RMS transitioning from aCD20 therapy

	Endpoint(s) for primary objective(s) 

No change or a reduction from baseline in the number of gadolinium enhancing lesions observed by MRI at 12 months of ofatumumab treatment (yes, no)

Secondary objective(s) 

Characterize participants retention, immune biomarkers, treatment satisfaction, and safety and tolerability at 6 and 12 months after transitioning to ofatumumab

	Endpoint(s) for secondary objective(s) 

Retention on ofatumumab treatment from baseline to Month 6 and to Month 12 (Yes, No)

Change from baseline in lymphocytes, including total CD19+ B cell counts and CD20+CD3+ T cell counts, obtained by fluorescence activated cell sorting (FACS) at Months 6 and 12

C-SSRS at Months 6 and 12

Objectives(s)	Endpoint(s)
	

• Treatment Satisfaction Questionnaire for Medication (TSQM-9) scores (including domains) at baseline vs Month 6 and vs Month 12

• Treatment-emergent adverse events

## 2 Statistical methods

### 2.1 Data analysis general information

The statistical analysis outlined in this SAP will be performed by Novartis Business Services (NBS) CONEXTS, using SAS® version 9.4 or higher software, and stored in the Novartis Global Programming and Statistical Environment (GPS).

It is planned that the data from all centers that participate in this protocol will be used for analysis.

For continuous variables, summary statistics will include number of participants (n), mean, standard deviation, minimum, 25th percentile, median, 75th percentile, and maximum.

For categorical variables, frequency counts and percentages will be reported.

Unless otherwise specified, summary statistics tables will include change from baseline.

The study will be divided into two phases (the core and post-treatment safety FU phase) for the purpose of preparing the CSR.

- **Core phase:** The core phase will cover the on-treatment period up Month 12 visit date, or EOS date plus the 30 day Safety Telephone FU for participants who discontinue prematurely. The primary objective will be analyzed for the core phase and will be reported in the analysis CSR. All data up to this date will be reported in the analysis CSR.
- **Post-treatment phase:** The post-treatment phase will cover the post-treatment safety follow-up period which extends from the EOS (+ every 3 months) until the date of B cell repletion for study completers until the participant initiates a commercial MS disease modifying therapy or until the end of the safety follow-up for premature withdrawals. This overlaps with the 30 day Safety Telephone FU. All safety data from the EOS to 30 day Safety Telephone FU will be reported as part of the core phase. Post-treatment phase will be reported in the final CSR. Data collected during the post-treatment safety FU will be listed.

## 2.1.1 General definitions

### 2.1.1.1 Investigational treatment/investigational drug

The investigational treatment is open label ofatumumab 20 mg (20 mg/0.4 ml) provided in an auto injector for subcutaneous administration. The investigational drug will be supplied by Novartis. Throughout the remainder of this document the investigational treatment will be referred to as study treatment/study drug.

### 2.1.1.2 Date of first/last administration of study treatment

The **date of first administration of study treatment** is defined as the first date when a non-zero dose of study treatment is administered and recorded on the “Study Treatment - Injection” electronic Case Report Form (eCRF).

The **date of last administration of study treatment** is defined as the last date when a non-zero dose of the study treatment is recorded on the “Study Treatment - Injection” eCRF.

### 2.1.1.3 Study day

The first day of administration of study treatment (first dose) is defined as *Study Day 1* or *Day 1*. All other study days will be labeled relative to Day 1.

For event dates **on or after Day 1**, study day for a particular event date is calculated as:

$$(\text{Date of event} - \text{date of first dose}) + 1$$

I.e., Day 2, Day 3, etc., will be one day, two days, etc., after Day 1, respectively.

For dates **before Day 1**, study day for an event date is calculated as:

$$(\text{Date of event} - \text{date of first dose})$$

**Duration of an event** will be calculated as (event end date – event start date + 1).

The descriptor “Day 0” will not be used.

#### **2.1.1.4 1 month**

For reporting of event durations and determining target days of scheduled visits, 1 month will be considered as  $365.25/12=30.4375$  days.

Unless specified otherwise, study days will be reported to the nearest whole number.

#### **2.1.1.5 Screening, baseline and post-baseline definitions**

**Screening** refers to any procedures (e.g., checking inclusion and exclusion criteria) performed prior to the date of the first dose of study treatment. Per protocol, participant informed consent must be obtained prior to performing any study related activity. The date of signing of informed consent is the start date of the screening period. Any assessment obtained during the screening period will be labelled screening assessment.

**Baseline** is the last assessment (including unscheduled visits) obtained before the first administration of the study treatment. No visit windows will be needed for the identification of baseline assessment. All assessments obtained after the first administration of study treatment are considered as **post-baseline** unless otherwise specified.

For blood pressure **vital sign values**, the baseline is the average of the non-missing values of the 3 measurements taken on the last visit prior to the first administration of study drug.

#### **2.1.1.6 On-treatment period (efficacy analyses)**

The on-treatment period for efficacy analyses is defined as:

$$(\text{Last study treatment administration date} - \text{first study treatment administration date}) + 31.4375$$

The on-treatment period definition applies to efficacy analyses only. This definition considers that participants are scheduled to administer the study drug once monthly.

#### **2.1.1.7 Post-treatment safety follow-up period**

The post-treatment safety follow-up period is defined as:

$$(\text{Date of B cell repletion} - \text{last actual study treatment administration date}) + 1, \text{ for study completers}$$

*Or*

$$(\text{Date of initiation of a commercial MS disease modifying therapy} - \text{last actual study treatment administration date}) + 1$$

#### **2.1.1.8 Efficacy analysis cut-off**

The efficacy analysis cut-off date is 30.4375 days after the date of last study treatment administration.

### **2.1.1.9 Safety analysis cut-off**

The safety analysis cut-off is the same as the efficacy analysis cut-off. The safety analysis cut-off is 30 days after the treatment end date but for programming purposes 30.4375 days will be used.

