9.3 Study completion and post-study treatment

Study completion is defined as when the last participant finishes their Study Completion visit and any repeat assessments associated with this visit have been documented and followed-up appropriately by the Investigator or, in the event of an early study termination decision, the date of that decision.

A participant is considered to have completed the study when they fulfill the following criteria:

- Participant has completed the study in its entirety according to the approved duration of the study within that country

- The participant has **not** stopped the study due to one or more of the following reasons:
 - Discontinuation of study treatment (Section 9.1.1)
 - Withdrawal of informed consent (Section 9.2)
 - Lost to follow-up (Section 9.1.3)

End of Study (EOS) visit is mandatory for all participants. For participants that complete the study, the next (and last) scheduled visit is the EOS visit and should align with the overall visit schedule. Participants will then enter the Safety Follow-up according to the assessment schedule in Table 8-2 if they do not initiate a commercial MS disease modifying therapy. Participants who prematurely discontinue study treatment will have their EOS visit as soon as possible and continue into the Safety Follow-up for 6 months according to the assessment schedule in Table 8-2 if they do not initiate a commercial MS disease modifying therapy.

The Investigator must provide follow-up medical care for all Participants who are prematurely withdrawn from the study, or must refer them for appropriate ongoing care.

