2 = moderate: sufficiently discomforting to interfere with normal activities

3 = severe: prevents normal activities

4 = life-threatening

- Its relationship to the study treatment.
- Its duration (start and end dates) or if the event is ongoing, an outcome of not recovered/not resolved must be reported
- Whether it constitutes a SAE (see [Section 10.1.2](#) for definition of SAE) and which seriousness criteria have been met
- Action taken regarding with study treatment

All adverse events must be treated appropriately. Treatment may include one or more of the following:

- No action taken (e.g. further observation only)
- Drug interrupted/withdrawn
- Concomitant medication or non-drug therapy given
- Participant hospitalization/participant's hospitalization prolonged (see [Section 10.1.2](#) for definition of SAE)
- Its outcome (not recovered/not resolved; recovered/resolved; recovered/resolved with sequelae; fatal; or unknown).

Conditions that were already present at the time of informed consent should be recorded in medical history of the participant.

Adverse events (including lab abnormalities that constitute AEs) should be described using a diagnosis whenever possible, rather than individual underlying signs and symptoms.

Adverse event monitoring should be continued following the last dose of study treatment until the participant starts a commercially available MS disease modifying therapy or until their B cells are repleted. Repletion is defined as a concentration > the participant's baseline value prior to starting the IV anti-CD20 mAb or > the lower limit of normal, whichever is observed first.

Once an adverse event is detected, it must be followed until its resolution or until it is judged to be permanent (e.g. continuing at the end of the study), and assessment must be made at each visit (or more frequently, if necessary) of any changes in severity, the suspected relationship to the interventions required to treat it, and the outcome.

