12.5.2 Safety endpoints

For all safety analyses, the safety set will be used. All listings and tables will be presented by treatment. Unless explicitly otherwise stated, only data up to and until B cells are repleted after the final study drug administration for study completers or until the participant initiates a commercial MS disease modifying therapy or until the end of Safety Follow-up for premature withdrawals will be included in the analysis and data beyond this time point for a participant will be excluded from safety analysis. In addition, a separate summary for death including on treatment and post treatment deaths will be provided. In particular, summary tables for adverse events (AEs) will summarize only on-treatment events, which started or worsened during the on-treatment period (treatment-emergent AEs).

The on-treatment period for safety analysis lasts from the date of first administration of study drug until B cells are repleted after the date of the last actual administration of study drug for study completers or until the participant initiates a commercial MS disease modifying therapy or until the end of Safety Follow-up.

Adverse events

All information obtained on adverse events will be displayed by treatment and participant. The number and percentage of participants with AEs of special interest/related to identified and potential risks will be summarized in the following ways:

[figure not shown]
- By treatment, primary system organ class and preferred term.
- By treatment, primary system organ class, preferred term and maximum severity.
- By treatment, pre-defined topic of interest, primary system organ class and preferred term.

Separate summaries will be provided for study medication related adverse events, serious adverse events, and other significant adverse events leading to discontinuation.

The number and percentage of participants with adverse events of special interest will be summarized by treatment, primary system organ class and preferred term. A participant with multiple AEs within a category is only counted once towards the total of that category.

Vital signs

All vital signs data may be listed by participant, and visit. Abnormalities will be flagged. Descriptive statistics for change from baseline will be provided by visit.

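### The SAP closes the AE and SAE tables 30 days after the last dose, the protocol keeps them open to B-cell repletion, DMT start or end of Safety Follow-up, and the SAP declares no change

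*SAP*

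**What the plan says.** **Protocol.** Section 12.5.2 states that "summary tables for adverse events (AEs) will summarize only on-treatment events, which started or worsened during the on-treatment period". It then defines that period: "The on-treatment period for safety analysis lasts from the date of first administration of study drug until B cells are repleted" after the last dose for completers, or until a commercial MS DMT is started, or until Safety Follow-up ends. Data collection matches this. Section 10.1.1 says "Adverse event monitoring should be continued following the last dose of study treatment until the participant starts a commercially available MS disease modifying therapy"; B-cell repletion is the alternative end-point there. Section 9.3 has premature discontinuers without a DMT "continue into the Safety Follow-up for 6 months according to the assessment schedule" in Table 8-2. Section 3 has completers without a DMT seen every 3 months until repletion or a new therapy.

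**SAP.** Section 2.1.1.9 equates the safety cut-off with the efficacy cut-off, which is counted from the last dose, and adds: "The safety analysis cut-off is 30 days after the treatment end date but for programming purposes 30.4375 days will be used". Section 2.8 admits only data before that cut-off to the safety analyses, and section 2.8.1 puts 30 days after treatment end into the TEAE definition. For what comes later, section 2.1 says "Data collected during the post-treatment safety FU will be listed". The time from last dose to repletion or DMT start, which the protocol counts as on-treatment for safety, is labelled post-treatment follow-up in section 2.1.1.7. Deaths are the exception: section 2.8.1.3 tabulates all of them. Table 4-1, the place for changes to protocol-specified analyses, reports none.

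**The concern.** TEAEs are a listed secondary endpoint, and the protocol keeps collecting AEs after the last dose in order to count them. Under the SAP, a non-fatal AE or SAE that starts more than 30 days after the last dose in a participant without a DMT is treatment-emergent by the protocol but absent from every summary table. For a participant who moves quickly to a commercial DMT the error can go the other way: the SAP window has no truncation at DMT start, so it can count events that fall outside the protocol period. A reader who sees no changes in Table 4-1 will take the tables as following the protocol definition.

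Three related defects make the window hard to program as written:

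- No on-treatment period for safety is defined. Of the one in section 2.1.1.6 the SAP says "The on-treatment period definition applies to efficacy analyses only", yet section 2.8.1.3 has to separate on-treatment from post-treatment deaths.
- The cut-off is tied to the last dose and the 30-day call to the EOS visit, so the cut-off can precede a call for which section 2.1 says "All safety data from the EOS to 30 day Safety Telephone FU will be reported as part of the core phase".
- The TEAE sentence in section 2.8.1 joins its two date limits with *or*. Read literally, an AE that started before the first dose passes the date test, and so does one long after the last dose.

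**Working it through.** **1. The definitions side by side**

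| | Protocol 12.5.2 | SAP |
|---|---|---|
| Start | First dose | First dose (2.8.1) |
| End | B-cell repletion, commercial DMT start, or end of Safety Follow-up | Last dose + 30.4375 days (2.1.1.8, 2.1.1.9); 30 days in 2.8.1 |
| Later non-fatal AEs and SAEs | Tabulated to the end of the period | Listed (2.1) |
| Deaths | Separate summary, on- and post-treatment | Same (2.8.1.3) |
| Declared as a change | n/a | No (Table 4-1) |

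The SAP document history records an updated TEAE definition (Amendment 1.0) and an updated safety cut-off (Amendment 2.0). Neither entry says that the result differs from the protocol.

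**2. Cut-off day.** The SAP's month reproduces: 365.25/12 = 30.4375 days. SAP Table 2-1 puts Month 11 at day 336 and Month 12 at day 366.

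- Last dose at Month 12: 366 + 30.4375 = day 396.4.
- Last dose at Month 11: 336 + 30.4375 = day 366.4.

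Both are shown because the protocol is unclear. Table 8-1 marks site administration at Month 12 and Table 8-4 has a pre-dose ECG there, while footnote 22 of Table 8-1 names only Months 1 and 6.

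**3. Time lost from the tables, completer without a DMT.** SAP Table 2-2 puts Safety Follow-up visits 1 and 2 at days 458 and 549.

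| Last dose | Followed to | Days after last dose | Share covered | Days not tabulated |
|---|---|---|---|---|
| Month 12 | Day 458 | 92 | 30.4375/92 = 33.1% | 61.6 |
| Month 12 | Day 549 | 183 | 30.4375/183 = 16.6% | 152.6 |
| Month 11 | Day 458 | 122 | 30.4375/122 = 24.9% | 91.6 |
| Month 11 | Day 549 | 213 | 30.4375/213 = 14.3% | 182.6 |

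The windows for these two visits (days 428 to 503 and 504 to 594) open after either cut-off, so no non-fatal event starting in them reaches a table for such a completer.

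**4. Early discontinuer followed to EOS + 6 months.** Days not tabulated = (6 × 30.4375 − 30.4375) + lag from last dose to EOS = 152.2 + lag. With an assumed lag of 0 to 37 days this is about 152 to 189 days.

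**5. Person-years.** The number entering Safety Follow-up is not in the documents. Each entrant followed to day 549 contributes 152.56/365.25 = 0.418 (Month 12) or 182.56/365.25 = 0.500 (Month 11) untabulated years.

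| Assumed entrants of 100 | Last dose Month 12 | Last dose Month 11 |
|---|---|---|
| 10 | 4.2 | 5.0 |
| 20 | 8.4 | 10.0 |
| 30 | 12.5 | 15.0 |

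For scale, 100 participants treated for 12 months give about 100 person-years.

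**6. Opposite direction.** If a DMT starts k days after the last dose (k below 30), the SAP window is 30.4 − k days longer than the protocol's.

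**7. Cut-off against the 30-day call** (target day 396 in SAP Table 2-1, window ±7 days).

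- Last dose at Month 11: 396 − 366.44 = 29.6 days before the call. Moving only the call (days 389 to 403) gives 22.6 to 36.6. If dose and EOS visit also shift by their 3 days each, the range is 16.6 to 42.6.
- Last dose at Month 12: cut-off and call coincide at target. The largest gap is 403 − 396.44 = 6.6 days, or 9.6 if EOS falls 3 days after the dose.

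**The case against.** The mismatch itself cannot be argued away, but its weight can. A 30-day window is a defensible choice. All AEs are listed, all deaths are tabulated, post-treatment data go into the final CSR, and the history does record that both definitions were updated. The study has one arm and no hypothesis test, so no comparison is biased. All of this stands and limits the consequence. It does not make the statement in Table 4-1 true.

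The figures are open to challenge too. Day 549 is one path: completers have no fixed six-month follow-up, and repletion or a DMT can end it sooner. That is right, and the percentages are illustrations. The path is still a real one, since Table 8-2 schedules the EOS + 6 months visit and protocol section 3 provides for participants not yet repleted at that visit. The person-years assume that every entrant is followed to day 549, and with few entrants they shrink towards zero. The comparator of 100 assumes that everyone completes and ignores the exclusion of site 1003.

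Two points of reading also deserve mention. Protocol section 12.5.2 joins its three end-points with *or* and does not say that the earliest applies, so the claim about early DMT starters rests on the natural reading. The *or* in SAP section 2.8.1 is very likely a slip. Read literally, it would leave section 2.8 as the only limit.

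**Conclusion.** The concern holds. The SAP replaces the protocol's safety period with a 30-day cut-off for the AE and SAE tables, including a secondary endpoint, and says that nothing changed. For a participant without a DMT followed to day 549, the tables cover 14% to 17% of the time after the last dose. For one followed only to day 458 they cover 25% to 33%. Participants who start a DMT within 30 days of the last dose lose nothing, and their SAP window may run too long. The total effect depends on how many enter Safety Follow-up and when they replete, neither of which is stated; the 4.2 to 15.0 person-years are scenarios for 10 to 30 entrants. Deaths and the primary endpoint are not affected. This should be fixed before the tables are produced.

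**What to change.** Choose one:

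- **A.** Use the protocol 12.5.2 period, with truncation at commercial DMT start, for the TEAE and SAE tables, and keep the 30-day version as an additional table.
- **B.** Keep the 30-day cut-off, declare it in Table 4-1 with a reason, and add one table of AEs and SAEs that start after the cut-off and before the end of the protocol's period.

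B is the smaller change and is sufficient. With either:

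- In section 2.8.1, replace *or* by *and* between the two date limits.
- Define an on-treatment period for safety, so that section 2.8.1.3 can classify deaths.
- State in section 2.1 how AEs between the cut-off and the 30-day call are shown.
- Have the protocol passages on a Month 12 dose (Table 8-1, its footnote 22, and Table 8-4) reconciled, since they set the anchor of the cut-off.

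The cost is SAP wording and one additional or re-run set of AE and SAE tables from data already collected. Follow-up after the last dose will differ between participants, so any table that extends past the cut-off needs person-years or a footnote on follow-up time beside the crude percentages.
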